## 4.7 Efficacy Evaluation

Typical-use 7-cycle pregnancy analyses will be done for the MITT populations, and perfect-use 7-cycle pregnancy analyses will be done for the EE population.

### 4.7.1 Analysis and Data Conventions

#### 4.7.1.1 Definition of Baseline

Baseline is defined as the last non-missing measurement on (prior to treatment) or before enrollment.

#### 4.7.1.2 Definition of Cycle

The cycle number will be derived from the eCRF menses start dates as follows:

Cycle 0 = date of enrollment through date before 1st menses started after enrollment (Note: this cycle includes cases where menses started on the day of enrollment)

Cycle 1 = date 1st menses started after enrollment through date before 2nd menses started after enrollment

Cycle 2 = date 2nd menses started after enrollment through date before 3rd menses started after enrollment

Cycle 3 = date 3rd menses started after enrollment through date before 4th menses started after enrollment

Cycle 4 = date 4th menses started after enrollment through date before 5th menses started after enrollment

Cycle 5 = date 5th menses started after enrollment through date before 6th menses started after enrollment

Cycle 6 = date 6th menses started after enrollment through date before 7th menses started after enrollment

Cycle 7 = date 7th menses started after enrollment through date before 8th menses started after enrollment

Cycle 8 = date 8th menses started after enrollment through date before 9th menses started after enrollment

If the subject became pregnant and the pregnancy adjudication committee estimated the date of conception, but the subject has no diary for the cycle that contains the estimated date of conception, then the pregnancy will be assigned to day 14 of the cycle. If partial start/end dates occur, then it will be assumed that the cycles were equal length to determine the imputed start/end dates of the cycle. If estimated date of conception could not be provided by the pregnancy adjudication committee due to insufficient information, then pregnancy will be assigned day 14 of the first potentially evaluable cycle after enrollment unless there is documentation to show the pregnancy occurred in a later cycle.

### 4.7.1.3 Multiple Comparisons/Multiplicity

This study has only one primary endpoint, no multiplicity adjustment is necessary.

### 4.7.1.4 Interim Analyses

No formal statistical interim analyses for efficacy are planned for this study.

### 4.7.2 Primary Efficacy Analysis

The primary efficacy endpoint is the cumulative percentage of typical-use 7-cycle pregnancy. The primary hypothesis to be tested is whether subjects using Amphora vaginal gel have a 7-cycle cumulative pregnancy percentage less than or equal to 21%, that is,

$$H_0: \pi_A > 21\% \text{ vs. } H_A: \pi_A \leq 21\%$$

where  $\pi_A$  represents the 7-cycle cumulative pregnancy percentage for Amphora. The Kaplan-Meier (KM) estimate and its 95% CI (based on Greenwood's method) of the 7-cycle cumulative pregnancy percentage of women in the MITT population will be calculated. If the upper bound of the 95% CI is  $\leq 21\%$ , then the null hypothesis will be rejected and the conclusion will be that the 7-cycle cumulative pregnancy percentage is  $\leq 21\%$ .

#### 4.7.2.1 Derivation of the Primary Endpoint

- a. The primary variable is the number of cycles from enrollment to the first pregnancy within seven cycles, which will be derived in the following steps:
  - Determining the evaluable cycles: Cycles must meet all conditions given below to be considered evaluable cycles:
    - Cycles 0-6 for subjects who are enrolled for at least 21 days prior to the start of her next menses (includes subjects who start menses on the day of enrollment), or Cycles 1-7 for subjects who are enrolled in less than 21 days prior to the start of her next menses;
    - Cycles that are indicated by the eDiary product use questionnaire that no backup contraception or EC are used or in which subjects become pregnant;
    - Cycles with length within the range of 21 days to 35 days or in which subjects have an on-treatment pregnancy.
    - Cycles where at least one entry of diary is recorded or in which subjects are pregnant.
    - Cycles must have at least one act of intercourse.
    - Cycles must start on or before date of last study product use + 7 days
    - For EE analyses, cycles in which the eDiaries indicate that study drug was used correctly for every act of intercourse during that cycle.

- Compressing the evaluable cycles: Evaluable cycles will be compressed to form contiguous evaluable cycles for each subject sequentially.
- Determining the date of conception:
  - The Pregnancy Review Committee will review all confirmed pregnancies except for subjects who had a borderline or positive b-hCG serum at enrollment, and this information will be provided to data management in an Excel file from the VCAS database. The committee will determine if the pregnancy occurred on-treatment (defined as date of conception between enrollment to <8 days after final study product use) or not on-treatment (defined as date of conception prior to enrollment or after 7 days following final study product use), or whether there is insufficient information for adjudication. The Pregnancy Review Committee assessment of pregnancies being on-treatment or not will be used for the primary endpoint. Pregnancies that could not be adjudicated due to insufficient information will be treated as on-treatment. The medical monitor will review the VCAS file and if the committee provided their own estimated date of conception in the “If disagree, provide rationale” field then the medical monitor will create a new column in the VCAS excel file and will enter into the new column the estimated date of conception provided by the adjudication committee in the “If disagree, provide rationale” field. This re-entry of the estimated date of conception will enable the programming of the statistical analysis.

For confirmed pregnancies, the date of conception will be assessed from the following:

- First trimester transvaginal ultrasound (considered the most accurate; later ultrasounds will not be used for redating)
  - Estimate based on pelvic and/or abdominal examination or pregnancy outcome
  - eDiary information (e.g., last menstrual period and sexual activity)
  - Quantitative  $\beta$ -hCG determination
  - Urine hCG (date of last negative and first positive)
  - Investigator estimation in the absence of above criteria
- Determining of censoring for cycles to pregnancy: Subjects will be censored from analysis at the earliest of:
    - The estimated date of conception that occurred between enrollment and <8 days after final study drug use
    - Date of last study product use + 7 days

- The conclusion of her seventh cycle on-treatment + 7 days (up to a total of 252 days [or 301 days for the sensitivity analysis, allowing a cycle length range of 21 to 42 days])

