9.8.1.1 Derivation of the Primary Variable

The primary variable is the number of cycles from enrollment to the first pregnancy within seven cycles, which will be derived in the following steps:

- Imputing the missing dates of cycles: If the eDiary has partial dates for the start/end of a cycle, then the dates will be imputed to be a full date (when possible) based on the start/end dates of cycles that occurred before and after that cycle with partial dates. If multiple cycles in a row occur with partial start/end dates, then it will be assumed the cycles were equal length in order to determine the imputed start/end dates of the cycle.
- Determining the evaluable cycles: Cycles must meet all conditions given below to be considered evaluable cycles:
 - Cycles 0-6 for subjects who are enrolled for at least 21 days prior to the start of her next menses, or Cycles 1-7 for subjects who are enrolled in less than 21 days prior to the start of her next menses;
 - Cycles that are indicated by the eDiary that no backup contraception or EC are used or in which subjects are pregnant;
 - Cycles with length within the range of 21 days to 35 days or in which subjects are pregnant.
 - For EE analyses, cycles in which the eDiaries indicate that study drug was used correctly for every act of intercourse during that cycle.
 - Compressing the evaluable cycles: Evaluable cycles will be compressed to form contiguous evaluable cycles for each subject sequentially.
- Determining the date of conception:
 - The Pregnancy Review Committee will review all confirmed pregnancies and determine if the pregnancy occurred on-treatment (defined as date of conception between enrollment to <8 days after final study product use) or not on-treatment (defined as date of conception prior to enrollment or after 7 days

following final study product use), or whether there is insufficient information for adjudication.

For confirmed pregnancies, the date of conception will be assessed from the following:

- First trimester transvaginal ultrasound (considered the most accurate; later ultrasounds will not be used for redating)
- Estimate based on pelvic and/or abdominal examination or pregnancy outcome
- eDiary information (e.g., last menstrual period and sexual activity)
- Quantitative β-hCG determination
- Urine hCG (date of last negative and first positive)
- Investigator estimation in the absence of above criteria

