- Determining of censoring for cycles to pregnancy: Subjects will be censored from analysis at the earliest of:
 - The estimated date of conception that occurred between enrollment and <8 days after final study drug use
 - The last date at which pregnancy status was known
 - The conclusion of her seventh cycle on-treatment (up to a total of 245 days [or 294 days for the sensitivity analysis, allowing a cycle length range of 21 to 42 days])

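### Protocol and SAP censor the primary endpoint by different rules with no stated reason, and neither says how a last cycle without a closing menses is credited

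*SAP*

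**What the plan says.** Both documents take the earliest of three dates, and they share only the first, the estimated date of an on-treatment conception.

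- **Second limb.** Protocol 9.8.1.1: "The last date at which pregnancy status was known". SAP 4.7.2.1: "Date of last study product use + 7 days".
- **Third limb.** Protocol 9.8.1.1: "The conclusion of her seventh cycle on-treatment (up to a total of 245 days". SAP 4.7.2.1: "The conclusion of her seventh cycle on-treatment + 7 days (up to a total of 252 days".

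SAP section 1 states that it is based on protocol version 4.0, the version reviewed here. The available SAP text has no section on changes from the protocol.

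The analysis unit is the cycle: "The primary variable is the number of cycles from enrollment to the first pregnancy within seven cycles". Protocol 9.8.1.1 admits "Cycles with length within the range of 21 days to 35 days or in which subjects are pregnant"; SAP 4.7.2.1 admits "Cycles with length within the range of 21 days to 35 days or in which subjects have an on-treatment pregnancy". SAP 4.7.1.2 says "The cycle number will be derived from the eCRF menses start dates as follows", and each cycle then runs to the day before the next menses. SAP 4.7.2.1 also requires a cycle to have begun no later than seven days after last use, a condition the protocol lacks.

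**The concern.** The estimate is judged against a fixed 21% bar, and about 48% of the primary population is expected to leave early, so how leavers are censored matters.

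The SAP limb has a good rationale. It matches the on-treatment definition (conception less than 8 days after last use) and removes time in which no countable pregnancy can arise. The protocol limb keeps such time: after early termination the exit visit, with its pregnancy test, falls 14-30 days after last use. But no SAP limb asks whether pregnancy status was known up to the censoring date. A woman who disappears can be counted as pregnancy-free for days that nobody verified.

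The length rule raises a second question. A last cycle that no menses closes has no length. Taken literally, it enters the analysis only if it holds a pregnancy, so events are added without the matching non-pregnant cycles.

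**Working it through.** **The plan's own figures.** Primary population: 1349 x (1 - 0.265) = 991. Cycles: 991.5 x 3.17 = 3143. Completers: 991.5 x (1 - 0.10 - 0.38) = 515, or 52%. Simulating 991 women with 16.5% pregnant by day 183, sequential dropout (0.90 x 0.62 retained) and a linear Greenwood limit gives 89.95% power against the stated 90%, with a standard error of 1.38 points. The caps are 7 x 35 = 245 and 245 + 7 = 252.

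**Why small shifts matter.** Power is Phi((21 - rate)/1.38 - 1.96). At 16.5% this is 90%; at 17.2% (+0.7) it is 79%; at 15.5% (-1.0) it is 98%.

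**Censoring limbs, day scale.** Assumptions: 28-day cycles; true rate 16.5% at day 196, so cumulative hazard -ln(0.835) = 0.1803; 10% dropout by day 28, then a constant rate to 52% retained; exit test uniform on days 14-30 after last use; for lost women, onset of the last menses is the last known status. The share of dropouts lost is not in the documents, so it is varied from 0 to 100%.

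| Dropouts lost | Protocol | SAP | Both limbs | SAP minus protocol |
|---|---|---|---|---|
| 0% | 15.8% | 16.5% | 16.5% | +0.7 |
| 25% | 16.0% | 16.2% | 16.5% | +0.3 |
| 50% | 16.1% | 16.0% | 16.5% | -0.2 |
| 100% | 16.5% | 15.4% | 16.5% | -1.0 |

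The two ends can be checked by hand. With dropout rates -ln(0.9)/28 = 0.00376 and -ln(0.52/0.9)/168 = 0.00327 per day, mean time on drug is 0.1/0.00376 + 0.38/0.00327, about 143 days. Adding 0.48 x 7 gives about 146 on-treatment days per woman.

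- Protocol, none lost: the exit test is on average 22 days after last use, so 15 days per dropout are off treatment. 0.48 x 15/146 = 4.9% excess exposure, and 1 - exp(-0.1803/1.049) = 15.8%.
- SAP, all lost: about 14 + 7 = 21 unverified days per dropout. 0.48 x 21/146 = 6.9% of pregnancies are missed, and 1 - exp(-0.1803 x 0.931) = 15.5%.

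At a true rate of 21%, where a pass should occur 2.5% of the time, simulated pass rates for 0/25/50/100% lost are 10.0/7.3/5.7/2.9% (protocol), 3.4/4.4/7.4/14.6% (SAP) and 2.9-3.4% (both limbs).

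**Sensitivity to the reading.** If the last scheduled test, not the last menses, is the last known status, the day-scale difference is about zero at 25% lost, -0.6 to -0.7 at 50% and -2.0 to -2.5 at 100%. On whole cycles with none lost, it is 0 if a closed cycle begun by last use + 7 days counts in full, and up to +0.85 if only cycles closed by that date count.

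**Open last cycle, cycle scale.** Risk per full cycle is 1 - 0.835^(1/7) = 2.54%; retention is as above; women leave at a random point in the cycle and none are lost.

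| Dropouts leaving an open cycle | Literal rule | Credited in full | Credited for time at risk |
|---|---|---|---|
| 100% | 17.2% | 15.8% | 16.5% |
| 50% | 16.8% | 16.1% | 16.5% |
| 25% | 16.7% | 16.4% | 16.5% |

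Hand check at 100%: 0.48 x 0.5 = 0.24 cycles of risk per woman produce events without exposure, against 4.87 closed cycles. That is 4.9%, and 1 - exp(-0.1803 x 1.049) = 17.2%.

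**Limits.** Every cycle before dropout is treated as evaluable (4.6-5.0 per woman against the planned 3.17). The absolute pass rates are therefore optimistic; the contrasts are the result.

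**The case against.** Five objections carry weight.

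1. **The two effects cannot both hold in full.** If the length rule is applied literally, a lost woman's open cycle contributes nothing, so her unverified days cannot lower the SAP estimate. With all dropouts lost, the literal reading returns 16.5%. This stands: the SAP's downward figures arise only when open time is credited. A reader might add the two effects; the rules do not permit that.

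2. **Dates and cycles are already linked.** A reader might infer that nothing connects them. In fact SAP 4.7.2.1 ties the start of a cycle to last use + 7 days, and SAP 4.7.1.2 maps dates to cycles. The gap is narrower: how to credit a cycle that the censoring date cuts, or that never closes. The partial-date imputation rules do not say that they cover a missing end date.

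3. **The open-cycle bias need not be upward overall.** This also stands. A dropout's closed last cycle is credited in full, which pushes the other way. Against day-level exposure, the net effect runs from about -0.4 to +0.8 points. Exit procedures for all early leavers should keep the open share well below 100%.

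4. **The extra seven days are mostly settled.** Evaluable cycles are limited to 0-6 or 1-7 and the endpoint to pregnancy within seven cycles, so a later conception appears not to count. If it did, 1 - 0.835^(203/196) = 17.0%, at most 0.5 points more. The extension then has no clear purpose and should be explained or dropped.

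5. **The SAP rule may simply be the better one.** In part it is. A reader might suspect that it was chosen to lower the rate; the documents do not support that, because with exit visits held it raises the estimate or leaves it unchanged.

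**Conclusion.** The discrepancy is a matter of text and needs no model: two censoring rules for one confirmatory endpoint, no stated reason, and no statement of which prevails. Each limb alone can bias the estimate low, the protocol's when leavers attend their exit test and the SAP's when they are lost and their open time is credited.

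Neither -1.0 nor -2.5 is a bound that the documents establish. Both depend on assumed loss to follow-up and on an undefined idea of known status, and a whole-cycle reading can give no difference when nobody is lost. The open-cycle point is an inference from the length rule, worth roughly +0.2 to +0.7 points over open cycles alone.

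Shifts of this size can move power between about 79% and 98% around the planned 90%, so the rule should be settled before analysis. It does not follow that the planned analysis is biased in a known direction.

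**What to change.** Write one rule in Protocol 9.8.1.1 and SAP 4.7.2.1:

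- **Event:** the estimated date of an on-treatment conception.
- **Otherwise censor at the earliest of** (a) the last date on which pregnancy status was known, defined as a negative test or onset of menses; (b) last product use + 7 days; (c) the end of the seventh study cycle.
- **Limb (c):** drop the extra seven days, or justify them and say whether a conception in them counts.
- **Unclosed last cycle:** apply one evaluability rule whether or not it holds a pregnancy, by crediting its time at risk up to the censoring date. Compute the Greenwood variance on the same risk set, and state how this works with compressed cycles.
- **Sensitivity analyses:** the current protocol rule, the current SAP rule and the literal open-cycle rule, each with the number of women and cycles affected.

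The cost is wording in two sections, one derived date and one exposure credit per woman from data already collected, and extra tables. Credited cycles fall slightly, from 5.0 per woman with whole-cycle credit to about 4.8, or 4.6 if all dropouts are lost. Using both limbs leaves a small upward bias if some lost women's pregnancies are still reported while their non-pregnant time is cut: the estimate reaches at most 16.9-17.0%, against a true 16.5%, when half are reported.

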### **4.7.3 Secondary Efficacy Analyses**

#### **4.7.3.1 Sensitivity Analysis with Respect to the Cycle Range**

The primary analysis will be repeated with the cycle length expanded from 21 – 35 days to 21 – 42 days.

#### **4.7.3.2 Sensitivity Analysis with Respect to the Dosing Time with Respect to Sexual Intercourse**

To evaluate the effect of the dosing time with respect to the time of sexual intercourse, the number and percentage of intercourse acts in the following categories will be shown:

- The number of intercourse acts where dosing time  $\leq$  1 hour before intercourse
- The number of intercourse acts where dosing time  $>$  1.5 hours but  $\leq$  2 hours before intercourse
- The number of intercourse acts where dosing time  $>$  2 hours but  $\leq$  2.5 hours before intercourse
- The number of intercourse acts where dosing time  $>$  2.5 hours before intercourse

The number and percentage of subjects in the following categories will also be shown:

- The number of pregnancies that occurred in a cycle where the longest duration from dosing time to intercourse was  $\leq$  1 hour
- The number of pregnancies that occurred in a cycle where the longest duration from dosing time to intercourse was  $>$  1 hour but  $\leq$  1.5 hours
- The number of pregnancies that occurred in a cycle where the longest duration from dosing time to intercourse was  $>$  1.5 hours but  $\leq$  2 hours
- The number of pregnancies that occurred in a cycle where the longest duration from dosing time to intercourse was  $>$  2 hours but  $\leq$  2.5 hours
- The number of pregnancies that occurred in a cycle where the longest duration from dosing time to intercourse was  $>$  2.5 hours

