4.4 Study Drug Use

Eligible subjects will receive study drug to use as their method of contraception while engaging in vaginal sexual intercourse. Study drug will be provided in a prefilled applicator containing 5-grams of drug.

Subjects will be instructed to administer a single pre-filled applicator of study drug intravaginally a maximum of one hour before each episode of vaginal intercourse. Additional applications of study drug should be administered before each additional act of vaginal intercourse regardless of the time of the last application (e.g., if vaginal intercourse occurs more than once in a day). If more than one hour passes before starting intercourse, an additional application of study gel must be applied.

Subjects should be encouraged not to douche during the study; however, if douching does occur, the subject should wait at least six hours after the last act of intercourse and should record the product used as a concomitant medication in the eDiary. Similarly, subjects should be advised not to use lubricants or other vaginal preparations before or during intercourse. If use does occur, it should be recorded in the eDiary and as a concomitant medication.

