9.8.3 Sensitivity Analyses

Sensitivity Analysis with Respect to the Cycle Range: The primary analysis will be repeated with the cycle length expanded from 21-35 days to 21-42 days.

Sensitivity Analysis of the Dosing Time with Respect to Sexual Intercourse: To evaluate the effect of the dosing time with respect to sexual intercourse, subgroup analyses for the primary analysis will be performed by the dosing time category performed according to the following

dosing time categories with respect to sexual intercourse: < 1 hour, < 1.5 hour, < 2 hours, <2.5 hours, and all cycles (without respect to dosing time).

Sensitivity Analysis with Respect to Completers and Non-completers: To evaluate differences between completers and non-completers the primary analysis will be repeated for just completers. A completer is defined as a woman who becomes pregnant within 7-cycles (inclusive) or who completes the 7 cycles with no pregnancy.

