#### **4.7.3.3 Perfect-Use 7-Cycle Pregnancy Probabilities**

As a secondary evaluation of contraceptive efficacy, the 7-cycle cumulative pregnancy percentage of women in the EE population will be estimated by KM method. Each woman in the EE population is evaluated for efficacy for menstrual cycles when she has used the study product consistently and correctly as reflected in her diary recordings. Non-perfect-use and non-evaluable cycles will be removed from the analysis. The perfect-use analysis will use the same conventions and analysis rules mentioned for the typical-use analysis, except that non-perfect cycles with a pregnancy will not be included. Greenwood's method for calculating variance will be used to construct 95% confidence intervals.

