#### **4.7.3.5 Summary of Number of Diary Cycles and Cycles Excluded from EE Population**

The average number of diary cycles will be summarized for all MITT subjects through seven cycles. Diaries where backup contraception or EC were used will be excluded unless the subject became pregnant in that cycle. The number of cycles with incorrect use of study product which result in exclusion from the EE analysis will be calculated for each subject and summarized descriptively.

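### The SAP's dosing-time table omits acts at >1 to ≤1.5 hours and bands cycles only when a pregnancy occurred, so it cannot show whether later dosing goes with more or fewer pregnancies (minor)

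*SAP*

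**What the plan says.** Protocol 4.4 tells subjects to apply the gel "a maximum of one hour before each episode of vaginal intercourse". Protocol 9.8.3 then plans that "subgroup analyses for the primary analysis will be performed by the dosing time category performed according to the following" categories: <1, <1.5, <2 and <2.5 hours, "and all cycles (without respect to dosing time"). These categories are nested. The protocol gives no rule for a cycle containing several acts with different intervals.

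SAP 4.7.3.2 keeps the aim of evaluating the effect of dosing time but plans two sets of counts:

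- **Acts.** It states that "the number and percentage of intercourse acts in the following categories will be shown", and lists four bands: ≤1, >1.5 to ≤2, >2 to ≤2.5 and >2.5 hours.
- **Pregnancies.** It lists "The number of pregnancies that occurred in a cycle where the longest duration from dosing time to intercourse was" in each of five bands, this time including >1 to ≤1.5 hours.

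SAP 6.1 assigns both to Table 14.2.3 in the MITT population. The SAP gives no reason for replacing the protocol's analyses.

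Three other sections bear on the point. For the perfect-use Kaplan-Meier (KM) analysis, SAP 4.7.3.3 says: "Each woman in the EE population is evaluated for efficacy for menstrual cycles when she has used the study product consistently and correctly". SAP 4.7.3.5 says: "The number of cycles with incorrect use of study product which result in exclusion from the EE analysis will be calculated for each subject", but not by interval. SAP 4.6 includes the >1 to ≤1.5 hour band in its summary of departures from instructions (Table 14.1.17), for the Safety population and without pregnancies.

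**The concern.** To evaluate an effect of dosing time on pregnancy, the table must compare how often pregnancy occurs in cycles with on-time and with later dosing. Pregnancies are banded by a property of the cycle, its longest interval, so the matching denominator is the number of evaluable cycles with that property. It is not planned. SAP 4.2 takes percentages over non-missing observations, so the percentage beside each count is a share of those observations and not a rate among cycles at risk in the band.

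The first late band, just beyond the instructed hour, also has no row in the act list.

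Two kinds of cycle have no stated place. SAP 4.6 recognises acts without gel, which have no dosing interval. A pregnancy in a cycle mixing such acts with on-time gel acts could be counted as ≤1 hour. SAP 4.7.1.2 keeps pregnancies from cycles without a diary, and these have no interval at all.

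What is at stake is whether this one table can support a statement about late dosing.

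**Working it through.** **1. Bands side by side**

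| Interval (hours) | SAP 4.7.3.2, acts | SAP 4.7.3.2, pregnancies | SAP 4.6, departures |
|---|---|---|---|
| ≤1 | yes | yes | not a departure |
| >1 to ≤1.5 | **no** | yes | yes |
| >1.5 to ≤2 | yes | yes | yes |
| >2 to ≤2.5 | yes | yes | yes |
| >2.5 | yes | yes | yes |

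One band is missing, and only from the act list.

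**2. What remains of protocol 9.8.3**

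- All cycles: this is the primary MITT analysis (SAP 4.7.2, Table 14.2.1).
- <1 hour: approximated by the perfect-use analysis (SAP 4.7.3.3, Table 14.2.4). The match is not exact, because that analysis also removes cycles with gel-free acts.
- <1.5, <2 and <2.5 hours: no counterpart.

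**3. A count without its denominator**

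SAP 4.7.3.2 states no figure to reproduce, so the inputs come from the sample-size section (SAP 4.11.1): 1349 enrolled, 26.5% not qualifying, 3.17 evaluable cycles per qualifying subject, 16.5% pregnant. The stated 3143 cycles reproduce: 1349 × 0.735 × 3.17 = 3143.1. The SAP calls these cycles evaluable for safety, but the product uses the efficacy inputs, and I use it as the number of efficacy cycles.

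Taking 16.5% as the seven-cycle risk, constant by cycle:

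- Per-cycle risk = 1 − 0.835^(1/7) = 2.54%.
- Expected pregnancies = 0.02543 × 3143.1 ≈ 80 (79.93).

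Assume 10 of these fall in one late band holding a share s of cycles. The band rate is 10 / (3143.1 s) and the rate elsewhere is 69.93 / (3143.1 (1 − s)).

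| Share s of cycles | Band rate | Rate in other cycles | Ratio |
|---|---|---|---|
| 5% | 6.36% | 2.34% | 2.72 |
| 10% | 3.18% | 2.47% | 1.29 |
| 20% | 1.59% | 2.78% | 0.57 |
| 30% | 1.06% | 3.18% | 0.33 |

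The same count fits a higher or a lower risk, and the planned table does not report s.

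**4. Act percentages cannot stand in for s**

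If a share p of acts is late, independently between acts, a cycle with k acts has a longest interval above one hour with probability 1 − (1 − p)^k. Protocol 4.1.1 requires willingness to have at least three acts per cycle, so take k = 3, and k = 10 as an assumed upper value:

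| p | k = 3 | k = 10 |
|---|---|---|
| 5% | 14.3% | 40.1% |
| 10% | 27.1% | 65.1% |
| 20% | 48.8% | 89.3% |

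**5. Limit of a crude rate by band**

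Use the same model with k equally likely from 3 to 10 and an assumed risk of 0.004 per act whatever the timing, so there is no true timing effect. Late and on-time cycles then have these per-cycle rates:

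| p | Late cycles | Late rate | On-time rate | Ratio |
|---|---|---|---|---|
| 5% | 27.9% | 2.84% | 2.46% | 1.15 |
| 10% | 48.1% | 2.80% | 2.35% | 1.19 |
| 20% | 73.4% | 2.73% | 2.13% | 1.28 |

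Late cycles contain more acts (7.1 against 6.0 on average at p = 10%), which alone raises their rate.

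**The case against.** The strongest reply is that the documents never promise a rate for each late band. The protocol's categories are nested, so restoring them would give rates up to each cut-off and not rates for separate late bands. The exploratory objective concerns dosing-time deviations among pregnancies, and the second list meets it. This stands. What remains is that SAP 4.7.3.2 states a wider aim than that objective, and protocol 9.8.3 planned rates where the SAP plans counts.

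A reader might infer that the SAP drops the whole dosing-time analysis of protocol 9.8.3. It does not, as step 2 shows. The MITT and perfect-use Pearl rates (SAP 4.7.3.4) could also, if their numerators and denominators are shown, yield by subtraction a rate for cycles outside perfect use. That contrast mixes late and gel-free use and is not banded.

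A reader might also infer that acts at >1 to ≤1.5 hours are reported nowhere. SAP 4.6 reports them for the Safety population. If the act percentages in Table 14.2.3 are taken over all acts with a known interval, the missing share is the remainder to 100%. The gap reads as a dropped line, and nothing in the documents suggests it was deliberate.

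Nor does the SAP say that gel-free cycles will be counted as on time; it leaves the case open. For missing diaries, SAP 4.2 would remove them from percentages but does not say how they are displayed.

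Finally, step 5 shows that a crude rate by band can suggest a timing effect where none exists. This is a fair argument for labelling such rates descriptive and showing acts per cycle beside them. It does not make counts without a denominator informative about an effect.

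**Conclusion.** The point holds and is minor. From the text alone, one act band is missing, and cycles are banded only when a pregnancy occurred. Table 14.2.3 therefore cannot show whether pregnancy is more or less frequent with later dosing. In effect three of the protocol's five dosing-time analyses are lost without explanation.

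No magnitude can be derived from the documents. The ratios of 0.33 to 2.72 show only that a count of pregnancies leaves the direction open. They rest on an assumed count of 10 in the band, assumed band shares and a constant per-cycle risk. The act model rests on assumed late-act shares, acts per cycle, independence and per-act risk.

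It would be wrong to infer that the primary result is in doubt. The KM estimate and its test against 21% use no dosing interval, and the sample size is not touched. The consequence is confined to this one table.

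**What to change.** In SAP 4.7.3.2 and Table 14.2.3:

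1. Add the >1 to ≤1.5 hour row to the act list.
2. Classify every evaluable MITT cycle, pregnant or not, by its longest gel-to-intercourse interval. For each band report pregnancies over cycles, a 95% CI and the mean number of acts per cycle.
3. Label these rates descriptive. The longest interval rises with the number of acts, and SAP 4.7.2.1 exempts pregnancy cycles from some evaluability conditions. One of those reads: "Cycles with length within the range of 21 days to 35 days or in which subjects have an on-treatment pregnancy". The backup-contraception and diary-entry conditions have similar exemptions.
4. Show cycles with any gel-free act, and pregnancy cycles without diary data, as separate rows so that neither is counted as ≤1 hour.
5. Preferably also run the protocol's <1.5, <2 and <2.5 hour KM analyses, assigning cycles by the same longest-interval rule. A sentence explaining their removal would document the change but would not repair the table.

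The cost is a little programming on eDiary times that are already collected. The CIs in the late bands will be wide, and the crude rates will remain confounded by act frequency.
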